treatment, concerns about logistically attending sessions, and appealing features of the treatment). Step five will include revising the treatment procedures and content based on the results from each cohort of development testing. Table 2 provides an overview of the timeline for Study 1.

Statistical Considerations. The primary goal of Study 1 is to develop MBRP-SA. Qualitative analysis of focus group will be the primary form of evaluation. The focus group will be audio-recorded and verbatim transcripts created for content analysis.¹⁵⁰ Using hand coding, the goal will be to identify key themes/textual units related to mindfulness and response to the treatment. Results from the qualitative interviews will be analyzed using the interview transcripts and content analysis. Content analysis will be conducted using an “intuitive” or “immersion/crystallizing” analysis plan, whereby the researcher reviews all data and pulls out those aspects most relevant to the research questions.¹⁵¹ The research team will identify key themes as they read through the interview transcripts. Descriptive statistics of quantitative measures will supplement the qualitative analysis. These may provide information for identifying aspects of implementation that require change prior to the feasibility study (Study 2).

Aim 2.

*Note: All procedures reported for Aim 2 will be conducted remotely, primarily via zoom and phone calls (but also via mailouts, emails, and text messages as appropriate). Group treatment sessions (MBRP-SA and CBT) will be conducted via zoom.

Project Overview. The primary goal of Study 2 is to measure benchmarks regarding the feasibility and acceptability of the MBRP-SA protocol created in Study 1. Participants (N=64) will be randomized to either MBRP-SA or CBT and tracked from 5 weeks pre-quit through 16 weeks post-quit. The first follow-up appointment will be a phone call scheduled at 8 weeks post-cessation (± 5 days). The second follow-up appointment will be a phone call scheduled at 16 weeks post-cessation (± 5 days). Table 4 provides a timeline of all procedures and assessments. Details are presented in the subsequent sections. Administering the battery of assessments below according to this timeline mimics the procedures for a future, large-scale R01 efficacy trial and will allow for the evaluation of feasibility for completing all procedures.

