^a = data collected during phone call (vs REDCap)

Phone Orientation Visit. Study personnel will call the participant at their scheduled session time and provide a detailed description of the study and obtain verbal consent. A copy of the informed consent and a PowerPoint describing the study in detail will be mailed and/or emailed to participants before the orientation session. If the participant decided to consent to the study, a series of self-report questionnaires to complete will be emailed to them (see Aim 3 below). Individuals who are ineligible or decline to participate will receive self-help materials and referrals for smoking cessation and alcohol use programs.

Zoom Orientation Visit. Consented participants will be scheduled for a group Zoom Orientation session one week before the first treatment session. Prior to the visit, participants will be provided a packet of instructions on how to access and navigate the video-conferencing app, Zoom, and additional materials related to the study (e.g. session handouts, welcome materials). Tablets, webcams, and/or microphones will be provided to participants on an as-needed basis. This orientation session will take place via Zoom. During this session, participants will be provided with a training on how to use video-conferencing app and will discuss the other relevant materials sent to participants in preparation for the first treatment visit. Prior to all Zoom visits in the study, participants will join a waiting room before they are admitted to the group, where they will see banners with reminders about sessions content, privacy standards, etc. This procedure will be followed for all treatment sessions as well as the Zoom Orientation session.

Randomization. Three stratification variables will be included: gender (men vs women), race/ethnicity (non-Hispanic White vs Other), and smoking rate (20+ cigarettes per day [CPD] vs less than 20). Within these 8 cells, eligible participants will be assigned to the two treatments using balanced-permuted block randomization with a block size of 4.

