Negative Affect/Depression/Stress/Anxiety Measures. Center for Epidemiological Studies Depression Scale (CESD) is a 20-item self-report questionnaire that assesses depressive symptoms experienced within the past week.¹⁶⁵ Distress Tolerance Scale (DTS) is a 15-item, Likert-scale self-report measure of an individual's perception of his/her own emotional distress tolerance.¹⁶⁶ Perceived Stress Scale (PSS) is a widely used self-report measure that assesses the degree to which participants find their lives to be stressful.¹⁶⁷ Positive and Negative Affect Scale (PANAS) is a 20-item self-report Likert-scale measure that assesses an individual's positive and negative affect at a given point in time.¹⁶⁸

Alcohol and Smoking Outcomes. Alcohol Use. The Timeline Followback (TLFB)¹⁷¹⁻¹⁷³ will be used to determine daily, recent alcohol use via retrospective self-report. A calendar is provided to participants, and they indicate any key events that occurred on certain dates to aid their memory. Participants then indicate how much alcohol they drank on each day. The TLFB has been widely used, evaluated, and has strong psychometric properties.¹⁷¹⁻¹⁷³ The TLFB will collect alcohol use from the past 4 weeks at the phone screen. The TLFB will be administered at each of the following visits and will ask participants to report their use since the last time they completed the TLFB: before visits 4 and 8, and at the 8-week and 16-week follow-up. From the TLFB, the primary outcome measure derived will be the percent of heavy drinking days (defined as: on a single occasion, ≥ 5 drinks for men and ≥ 4 drinks for women). Other alcohol use outcomes, such as percent days' abstinent and alcoholic drinks per drinking day, will also be derived.

Smoking Abstinence. To determine smoking abstinence, we will use the 7-day point prevalence, which is a combination of a self-report of no smoking in the last 7 days, combined with a biochemical verification of abstinence via saliva cotinine. Participants who report abstinence will be mailed a saliva cotinine kit to confirm abstinence at their 16-week follow-up call. The TLFB will be used to collect tobacco use throughout the study, and the schedule will mimic that used to collect alcohol use.

G. Data Management and Statistical Considerations for Study 2

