To ensure participant confidentiality, no unique identifiers will be recorded into the dataset to be analyzed. Data will be collected via REDCap. The entered and reviewed data will be transferred monthly to a SPSS database.¹⁷⁴

Sample Size. Randomizing 64 participants to MBRP-SA and CBT will provide sufficient data for assessing feasibility of the RCT, based on existing recommendations in the literature for sample size estimates in feasibility studies.^{175,176} A full set of statistical analyses focusing on treatment differences will be performed as part of the feasibility assessment. However, the sample size will not be sufficient for detecting treatment differences for anything less than large effect sizes (e.g., Cohen's $d \geq .72$) for simple, two-group comparisons of a continuous variable with $\alpha=.05$, power $\geq .80$, and a two-tailed test. Binary variables assessed under the same testing conditions would require an $OR \geq 5.95$.

Data Analysis Overview. Analyses will be conducted with SPSS and SAS version 9.4¹⁷⁴ and Mplus Version 7.¹⁷⁷ Descriptive statistics of demographics, smoking history, and alcohol history variables will be calculated and group comparisons will be performed. Descriptive statistics of all study measures (i.e., proximal and distal measures of alcohol use and smoking) will be calculated. Although underpowered to detect small- or medium sized sex differences, all analyses will examine sex as a covariate. Furthermore, analyses will include treatment group (i.e., each subset of participants who are treated with MBRP-SA or CBT together) when the intraclass correlation coefficient is > 0.10 .

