A similar approach to analysis will be taken for the primary outcomes (the distal measures). TLFB will be used to derive a measure of heavy alcohol use and the 7-day point prevalence will be created for smoking abstinence at five targeted 1-week periods prior to a session: start of treatment (week -4), quit date (week 0), end of treatment (week +3), and two follow-ups (week +8 and week +16). Descriptive statistics will be presented in figures. GEE with an AR(1) working correlation matrix ($r=.60$) will be used to assess the effects of treatment, time (-4, 0, +3, +8, +16), and their interaction on the primary outcome measures. Means, percentages, and 95% confidence intervals will provide useful guidance as we determine sample sizes for a full-scale RCT. There is not adequate power to detect small- to medium-sized treatment group differences given the sample size. However, we would interpret any within-subject decreases in the number of heavy drinking days from pre- to post-treatment and/or any within-subject increases in smoking abstinence as evidence that the MBRP-SA intervention may be beneficial for these two problematic health behaviors. Given the small sample size, these changes are not likely to be significant. However, sample means and standard deviations will provide valuable data for

estimating sample size in a large-scale RCT. Changes in craving, self-efficacy, and general use of alcohol and smoking will also be examined as proximal outcomes that will also inform the development of a large-scale trial.

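### The distal model appears to measure heavy drinking in five single weeks although the TLFB covers every day; longer windows would usually give more precise planning estimates

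*Combined protocol and SAP*

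**What the plan says.** Under Alcohol and Smoking Outcomes, "the primary outcome measure derived will be the percent of heavy drinking days". Heavy drinking is defined by a drink threshold for each sex, and no window length is given for the percentage. On collection, "The TLFB will collect alcohol use from the past 4 weeks at the phone screen". Each later TLFB (before visits 4 and 8, and at weeks +8 and +16) covers the time since the previous one. By design, daily coverage therefore has no gaps.

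The Aim 3 paragraph on the distal measures states that "TLFB will be used to derive a measure of heavy alcohol use". The same sentence creates 7-day point prevalence for smoking and refers to "five targeted 1-week periods prior to a session: start of treatment (week -4", followed by the quit date, the end of treatment and two follow-ups. One GEE specification with times -4, 0, +3, +8 and +16 then serves both outcomes. No reason is given for a 1-week period for alcohol.

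That paragraph also says that means, confidence intervals and SDs will guide the size of a full-scale trial, and that any within-person fall in heavy drinking days will be taken as a sign that MBRP-SA may help.

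**The concern.** Seven days is built into the smoking outcome. It is not built into percent heavy drinking days, which is a rate and is better estimated from more days. Eligibility (section 1.1) requires only one heavy occasion in the past month, so for lighter participants a single week says little.

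A percentage from seven days can take only eight values (0/7 to 7/7), and many will be zero. The sampling noise of one week is added to the real differences between people. That widens the intervals Aim 3 reports and raises the SD it passes on for planning. It also makes a change between two single weeks a weak basis for the within-person reading described above.

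**Working it through.** **Inputs from the documents.** "Participants (N=64) will be randomized to either MBRP-SA or CBT", in balanced blocks, so 32 per arm. Tracking runs from week -5 to week +16. The screening TLFB covers 28 days. There are five 1-week analysis periods. Entry requires at least one heavy occasion in the past month.

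**The plan's own figure.** The Sample Size section gives a detectable d of 0.72 at two-sided alpha 0.05 and power 0.80. It reproduces: 31 per arm suffice by the normal approximation, and with 32 per arm power is 0.821 (normal) or 0.809 (noncentral t). This figure is standardised, so the window does not change it. The window changes what 0.72 means in percentage points.

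**Days used.**
- Analysed: 5 × 7 = 35.
- Available: 21 × 7 = 147, or 147 + 28 = 175 with the screening month.
- Share used: 35/147 = 24% or 35/175 = 20%, so 76-80% of the days are outside the distal model.
- The four post-baseline periods use 4 × 7 = 28 days. Windows of weeks -4 to 0, 0 to +3, +4 to +8 and +12 to +16 would use 28 + 21 + 28 + 28 = 105.

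**Variance.** Let p be the mean daily rate and s the between-person SD, with days independent within a person. The variance of a k-day percentage (as a proportion) is v(k) = s² + (p(1-p) - s²)/k. The documents give neither p nor s, so both are assumed.

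| p | s | v(7) | v(28) | v(28)/v(7) |
|---|---|---|---|---|
| 0.10 | 0.20 | 0.0471 | 0.0418 | 0.886 |
| 0.20 | 0.20 | 0.0571 | 0.0443 | 0.775 |
| 0.40 | 0.15 | 0.0536 | 0.0303 | 0.565 |
| 0.20 | 0.30 | 0.1000 | 0.0925 | 0.925 |
| 0.30 | 0.30 | 0.1071 | 0.0943 | 0.880 |
| 0.40 | 0.30 | 0.1114 | 0.0954 | 0.856 |
| 0.10 | 0.30 | 0.0900 | 0.0900 | 1.000 |

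Over means of 10-40%, the reduction is 11-43% at SD 0.15-0.20. At SD 0.30 it is 7-14% for means of 20-40%. At mean 10% and SD 0.30, p(1-p) = s² = 0.09, so no day-to-day variance remains and nothing is gained. For the 21-day window before +3, the reduction at SD 0.15-0.20 is 10-39%.

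**Zeros.** A week nested in a 28-day window can never show fewer zeros, whatever the model. A person with exactly one heavy day in 28 has a 21/28 = 75% chance of none in a given week. For the sample share, take a beta-binomial with M = p(1-p)/s² - 1, a = pM and b = (1-p)M; the chance of zero in m days is B(a, b+m)/B(a, b). At p = 0.20, s = 0.20 (M = 3, a = 0.6, b = 2.4) it falls from about 43% in 7 days to 21% in 28. At s = 0.30 (M = 0.778) it falls from 61% to 49%.

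**What this means for planning.** At mean 20% and day-level ICC 0.2, between-person SD is √(0.2 × 0.16) = 0.179. With SD = √(p(1-p)[1 + (m-1)ICC]/m), the SD is 22.4 points for 7 days and 19.1 for 28. A d of 0.72 is then 16.1 or 13.8 points. For a 10-point difference, n per arm = 2[(1.96 + 0.84) × SD/10]² gives 79 or 58. At mean 20% and SD 0.30 the SDs are 31.6 and 30.4 points, and n is 157 or 146.

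**Relaxing independence.** In a simulation, each person's weekly rate drifts with week-to-week correlation 0.5, 0.8 or 0.95 (logit SDs 1.2 between people and 0.8 between weeks, mean about 26%). The SD moves from 0.266 to 0.215, 0.266 to 0.226 and 0.264 to 0.231. Squaring the ratios gives 35%, 28% and 23% lower variance. In the other direction, a person who drinks heavily every Saturday and on no other day scores 1/7 in any week and 4/28 over four, so for that person nothing is gained.

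**The case against.** **The sentence is ambiguous.** The 1-week phrase could attach to smoking alone. That reading is possible but less natural, because both outcomes then share the same five model times. If it is right, alcohol has no stated window and the text still needs completing.

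**No data are lost.** A reader might infer that most of the TLFB is thrown away. The documents do not support that. The daily records stay in the dataset, other alcohol outcomes are to be derived from them, and descriptive statistics are promised for all measures. Only the distal model leaves the days out. Nor is the 7-day SD wrong: it is correct for a 7-day outcome, and a 28-day SD can be computed later from the same records. What remains is that the planned model and its reported figures would be noisier than they need to be.

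**The gain may be small.** Entry runs from one heavy occasion a month to alcohol use disorder, which is not excluded, so a between-person SD of 0.30 is plausible. This objection stands, and the range above includes it.

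**Longer windows change the question.** They estimate average use over a period, not use at a time point. Drinking goals start at Session 5 and some people will cut down sooner, so averaging blends some change. This is a real cost.

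**The screening month is a poor outcome baseline.** It is tempting to use the 28 days before session 1 as the first outcome point. Under Telephone Screening, the screening TLFB confirms the alcohol entry criterion, so every entrant must have a heavy day in that month. Unless screening came at least four weeks before session 1, the windows overlap. Part of any later fall would then be regression to the mean, and the same days could serve as both outcome and covariate. This objection stands, and the fix avoids it.

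**Conclusion.** The point holds in a limited form. On its most natural reading, the plan fits the distal alcohol model to about 35 of 147-175 available days, with no reason given for one week. That can never reduce the zeros and usually raises the variance. With assumed means of 10-40% and between-person SD of 0.15-0.30, a 28-day window lowers variance by roughly 0-43%, and by less where drinking is stable or weekly-patterned. The size depends entirely on those assumptions, since the documents give no mean, SD or ICC. The week +3 window has only 21 days after the quit date, so the 28-day figures do not apply to it.

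A reader might infer that the study's main conclusions are at risk. They are not: the Table 5 benchmarks are the primary outcomes of Study 2, and Aim 3 is descriptive and declared underpowered. The consequence is less precise planning estimates, which a change of derivation can largely avoid.

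**What to change.** - **Smoking:** keep the 1-week periods.
- **Alcohol:** state the window explicitly. Compute percent heavy drinking days over all TLFB days in prespecified, non-overlapping post-baseline windows, for example weeks -4 to 0, 0 to +3 (21 days), +4 to +8 and +12 to +16.
- **Sensitivity:** report the planned 1-week values alongside.
- **Baseline:** use the 28-day phone-screen value only as a covariate in the arm comparison, not also as an outcome time point.
- **Pre-to-post description:** use days after screening and before session 1. The Zoom orientation is one week before session 1 and follows screening, so the plan's own week -4 period qualifies. Do not read a within-person fall from the screening month as evidence of benefit.
- **Planning:** report each mean and SD with its window length, so that the full-scale trial takes the SD that matches its own outcome.

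The cost is SAP wording and a changed derivation; no new data are needed. The downside is that the longer windows describe average use over a period and blend some change within it. The 1-week sensitivity values partly cover that.

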1. PARTICIPANT SELECTION

1.1 Eligibility Criteria

Aim 1: Inclusion criteria will be ≥ 18 years of age; currently smoking ≥ 3 cigarettes per day for the past year; carbon monoxide level ≥ 8 ppm; should carbon monoxide level yield a result less than 8 ppm, the participant will be asked to submit a urine sample to determine cotinine levels and the result must be \geq level 3 ; motivated to quit smoking and decrease alcohol use within the next 60 days; if male, consumes ≥ 5 drinks and if female, consumes ≥ 4 drinks on at least 1 occasion in the past month; willingness and ability to attend the 8 weekly group sessions; valid home address in the Tampa Bay area; functioning telephone number; and can speak, read, and write in English.

Aim 2: Inclusion criteria will be ≥ 18 years of age; currently smoking ≥ 3 cigarettes per day for the past year; motivated to quit smoking and decrease alcohol use within the next 60 days; if male, consumes ≥ 5 drinks and if female, consumes ≥ 4 drinks on at least 1 occasion in the past month; willingness and ability to attend the 8 weekly video group sessions; willingness and ability to use an email account for study materials; valid address; functioning telephone number; and can speak, read, and write in English.

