MBRP-SA Development. The primary adaptation for MBRP-SA will be to tailor some the session content and discussions to smoking cessation and alcohol use. These changes will be primarily guided by the existing literature (e.g., studies on mindfulness-based treatments for smoking cessation) and the experience/knowledge of the investigative team. It should be noted that MBRP already addresses some of the primary underlying mechanisms of smoking cessation and reduced alcohol use (e.g., managing negative affect and craving) and that the extant literature indicates that key behavior modification constructs (e.g., self-efficacy) are impacted by mindfulness.^{45,50,67,76} Therefore, we will not modify the core components of MBRP, but instead supplement the existing protocol with content unique to smoking and alcohol use.

Content Modifications. Content modifications listed here fall into 3 categories: smoking-specific, alcohol-specific, and co-use. Given MBRP has already demonstrated efficacy for reduced alcohol use, most of these modifications focus on smoking and co-use content. Modifications are based on the existing literature, ability of content to address underlying behavior-change mechanisms (e.g., motivation) and Co-I [name] experience developing and testing a mindfulness-based cessation intervention.⁵⁸ **SMOKING-SPECIFIC: Quit date.** Research regarding smoking cessation indicates that motivation can be enhanced by setting a specific quit date.¹⁴² Therefore, MBRP-SA will set the smoking quit date at Session 5, which is supported by existing mindfulness-based cessation treatments (e.g., ⁵⁸). This permits time for individuals to develop their mindfulness practice (Sessions 1-4) while still providing ongoing support for 3 weeks after the quit day. **Losing a friend.** Many smokers report that smoking a cigarette represents a type of "friendship" and that quitting smoking is like losing a close friend.¹⁴³⁻¹⁴⁵ MBRP-SA will acknowledge and process this type of cognition in Session 3. **Diet and Weight Gain.** Many individuals endorse motivation to continue smoking for weight control purposes,¹⁴⁴ and therefore we will include information on this topic in Session 3. **Nicotine Patch.** Current guidelines for smoking cessation indicate that when provided with a combination of nicotine replacement therapy and counseling, chances of success are greatest.¹⁴² Thus, participants will be

[figure not shown]

Figure 3. Treatment Development Flow

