provided with nicotine patches at the end of Session 4, with the intention to begin using them at Session 5. Psychoeducation about patch use will occur at Session 4. Mindful Smoking is a mindfulness activity that brings awareness to the act of smoking a cigarette. An introduction to this will occur at the end of Session 2, and the actual practice will be conducted right before the beginning of Session 3 group. Participants will be encouraged to continue mindful smoking until their quit day at Session 5. **ALCOHOL-SPECIFIC:** Reduced alcohol use. Alcohol use will be monitored at each treatment session. A discussion of goals related to reduced drinking will begin at Session 1 and continue through Session 5. Participants will be encouraged to set realistic drinking goals for themselves, which is consistent with a harm reduction approach to alcohol use and fits within the framework of social determination theory.^{146,147} Participants will be encouraged to implement drinking goals at Session 5 (to coincide with the smoking quit date), although many people may have already decreased use. At the orientation session, participants will be provided with a handout with psychoeducational information on alcohol use, and they will be encouraged to use this when deciding what their alcohol use goal will be. **CO-USE:** Psychoeducation on the health impacts of cigarette and alcohol use. Consistent with recommendations,¹⁴² participants will be provided with psychoeducation information on the impact of cigarette and alcohol use on their health at Session 1. Information on the benefits of quitting smoking and reducing drinking (e.g., breathing becomes easier, decrease risk of cancer development) will also be discussed and provided. Relationship between smoking and drinking. Given common underlying mechanisms of the co-use of alcohol and smoking exist (e.g., cue-induced craving, positive and negative reinforcement),¹¹⁻¹⁶ discussions related to the inter-connected relationship among smoking and alcohol use will be conducted. This discussion will also include a focus on previous attempts to change either or both behaviors by participants. We will also highlight that continued alcohol use may serve as a trigger for relapse. Discussions regarding whether complete abstinence is the best option for some participants will be conducted. We believe this added content will aid participants in making the best decision regarding their own co-use. These discussions will occur at Session 2.

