Table 5. Measureable Benchmarks

Area of Interest	Description of Outcome to be Evaluated	Measure and/or Expected Outcome
Acceptability	Participant Satisfaction	Client Satisfaction Questionnaire ¹⁵⁸ (satisfaction of ≥80%)
	Intention to continue to use skills learned from the treatments	Questionnaire developed for this study
	Perceived appropriateness of the treatments for smoking and alcohol use	Questionnaire developed for this study
Demand	Accrual rates for study	For recruitment, the cost of each participant will be ≤\$100
	Completed sessions	≥40% of participants will complete all 8 sessions; ≥60% will complete between 4 and 7 sessions*
	Homework Completion	For MBRP-SA, participants will engage in mindfulness homework at a minimum of 3.5 days per week*
Implementation/ Practicality	Screening/eligibility for study	Record number of call attempts for each participant and reasons for ineligibility
	Recruitment	Recruit 8 eligible participants per month; 60% of recruitment will be completed by the end of year 2
	Retention	Retain 80% through end of treatment, 70% through follow-up
	Questionnaire completion	For sessions attended, 90% of questionnaires will be completed

Note. * based on data from Bowen et al., 2014; Vidrine et al., 2016; Witkiewitz et al., 2014^{64,66,107}

Aim 3.

The primary goal of Aim 3 is to collect and examine descriptive data on proximal variables associated with smoking abstinence and reduced drinking (e.g., negative affect, craving), as well as distal variables (smoking abstinence, heavy alcohol use) from Study 2. Aim 3 will be underpowered to test for any main effects of treatment on clinical outcomes. Nonetheless collecting these data will contribute to our assessment of feasibility and will provide guidance as we determine the sample size for a full-scale efficacy trial.

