Aim 2 - Evaluate benchmarks regarding feasibility and acceptability. Feasibility will be assessed by the multiple indices described in Table 5. Each index will either be compared to published norms (e.g., CSQ) or our prior experience with clinical trials. We expect to recruit adequate numbers of eligible participants during the study timeframe with efficient cost expenditures, retain at least 80% through the end of treatment, and retain at least 70% through the end of the study. Treatment acceptance and satisfaction are expected to be 80% or higher, and participants are expected to comply with treatment requirements. The team will determine whether corrective actions for future studies are needed when an index suggests underperformance. Evaluation of all indices will inform and guide modification prior to the proposal of a full-scale RCT.

Aim 3 - Collect and examine descriptive data on proximal and distal variables associated with alcohol use and smoking. Descriptive statistics of proximal measures (e.g., negative affect, self-efficacy) will be presented in figures to review change over time and treatment differences. Generalized estimating equations (GEE) will be used to fit population-averaged models with the main variables of treatment, time, and their interaction. An AR(1) working correlation matrix will be used with $r=.70$. Covariates and potential confounding variables will be included, as warranted. This approach preserves data for analysis by avoiding listwise deletion of observations when at least one dependent variable was observed. Qualitative analyses (e.g., thematic analysis) may also be conducted on aspects of the treatment process.

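### The smoking-abstinence GEE includes two windows that precede the planned quit, so its overall time and interaction tests can be non-estimable or unreliable; arm contrasts after the quit are unharmed

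*Combined protocol and SAP*

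**What the plan says.** The analysis is in section 2, part G (Data Management and Statistical Considerations for Study 2), Aim 3. Seven-day point-prevalence abstinence is created for "five targeted 1-week periods prior to a session: start of treatment (week -4), quit date (week 0), end of treatment (week +3") and for weeks +8 and +16. A GEE with AR(1) working correlation r = .60 then assesses treatment, "time (-4, 0, +3, +8, +16), and their interaction on the primary outcome measures". No link, time coding or rule for empty cells is given. The same part would read "any within-subject increases in smoking abstinence as evidence that the MBRP-SA intervention may be beneficial".

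Three other places fix what the first two windows can contain:
- Section 1.1: entrants are "currently smoking ≥ 3 cigarettes per day for the past year".
- Content Modifications, Quit date: "MBRP-SA will set the smoking quit date at Session 5". Table 4 puts Session 5 and quit day at week 0 for both treatments.
- Content Modifications, Mindful Smoking: "Participants will be encouraged to continue mindful smoking until their quit day at Session 5". This applies to MBRP-SA only.

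Under Alcohol and Smoking Outcomes, abstinence is defined as self-report of no smoking for 7 days plus verification by saliva cotinine. The kit is sent only in connection with the 16-week call, and Table 4 has a single saliva mark. The Timeline Followback (TLFB) records tobacco use throughout.

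**The concern.** The weeks before the week -4 and week 0 sessions both end before anyone is asked to stop smoking. Abstinence there should be at or near zero in both arms by design. On the logit scale an empty arm-by-window cell has no finite estimate. A joint test of time, or of treatment by time, that includes such a cell then reflects where the software stops rather than the data.

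The same near-zero start undermines the plan's reading of change. Any quitting at all is an increase, in CBT as much as in MBRP-SA.

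The definition raises a separate point. It requires cotinine, so it cannot be met at +3 or +8 with the data collected.

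At stake are the Aim 3 time and interaction results for smoking and the sentence that interprets them. The Study 2 benchmarks in Table 5 are not involved.

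**Working it through.** **Inputs from the plan.** 64 randomised, taken as 32 per arm; five times; AR(1) r = .60; retention benchmark "Retain 80% through end of treatment, 70% through follow-up", so about 0.80 × 32 = 25.6 (26) per arm at +3 and 0.70 × 32 = 22.4 (22) at +8 and +16. The plan gives no abstinence rate. Its stated detectable effects do reproduce at 32 per arm: d = 0.72 has power 0.81, and OR 5.95 has power 0.80 at an assumed 10% base rate. They do not bear on this point.

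**1. Chance of an empty cell.** If true pre-quit abstinence is p, one arm of 32 has no abstainer in a given window with probability q = (1 - p)^32, and at least one of the two arms is empty with probability 1 - (1 - q)^2.
- p = 1%: q = 0.725; at least one arm empty 92%
- p = 2%: q = 0.524; 77%
- p = 5%: q = 0.194; 35%
- p = 10%: q = 0.034; 7%

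**2. What an empty cell does (logit link, categorical time).** The coefficient falls by about one log-odds unit per iteration. In one simulated data set with both pre-quit windows empty, the week -4 term was -7.2, -12.2 and -22.2 after 5, 10 and 20 iterations. The robust standard error does not grow with it. For a single cell of n people under working independence, with fitted probability m, the robust variance is n·m² / [n·m(1 - m)]² = 1/[n(1 - m)²], which tends to 1/n. With n = 32 the SE tends to 1/√32 = 0.18. A Wald statistic can therefore grow without limit when one arm is empty and the other is not.

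**3. Simulated fits.** Assumed abstinence at +3/+8/+16 was 25/20/15% (CBT) and 40/35/30% (MBRP-SA); latent-normal AR(1) 0.6; 1,000 trials per scenario. All coefficients were finite (converged, every |coefficient| below 10, every SE below 5, week -4 as reference) in 0%, 6% and 45% of trials at 0%, 2% and 5% pre-quit abstinence. With losses at the retention benchmarks the figures were 0%, 6% and 43%.

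**4. Joint interaction test with no arm difference** (25/20/15% in both arms, robust Wald, nominal 5%). Over different implementations and iteration limits, rejection was:
- 0% pre-quit: 2 to 10%
- 2% pre-quit: 16 to 76% (74 to 76% when stopped at 15 iterations)
- 5% pre-quit: 10 to 56% (54 to 56% when stopped at 15 iterations)
- three post-quit times only: roughly 2 to 8%

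A score test held its level (2 to 4%) but could not be computed in 48% of trials at 2% and 7% at 5%.

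**5. What survives.** Arm contrasts at +3/+8/+16 had median SEs of 0.55/0.59/0.64 in both the five-time and the three-time model. With complete data the estimates were the same.

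**6. If time is linear.** The model converges, but the slope mainly reflects quit day. For abstinence falling 40/30/20% after the quit, the slope is +0.038 log-odds per week with five times and -0.066 with three. For flat 30% it is +0.079 against about 0.

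**7. The reading of any increase.** Starting from zero, the chance that an arm shows at least one abstainer is 1 - (1 - p)^n.
- n = 32: 1 - 0.95^32 = 0.81 and 1 - 0.90^32 = 0.97
- n = 22: 1 - 0.95^22 = 0.68 and 1 - 0.90^22 = 0.90

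If both arms of 32 share the same true rate and are independent, both show an increase with probability 0.81² = 0.66 at 5% and 0.97² = 0.94 at 10%.

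**The case against.** Much can be said for the plan. It fixes neither link nor time coding, so the failure is conditional. With an identity link, which it does not exclude, interactions against a zero baseline are simply the post-quit arm differences. Some participants may quit early after four sessions, and mindful smoking is encouraged in one arm only. At exactly 0% the joint test is not inflated. The high rejection rates need a few pre-quit abstainers, and they vary with the iteration limit; none was run in the software the plan names. An analyst would not ordinarily report a fit flagged as not converged. The plan also calls Aim 3 descriptive and underpowered, and relies on means, percentages and confidence intervals to size the next trial. All of this stands, and it limits the point to the overall tests and the interpretive sentence.

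A reader might infer that the GEE cannot give any valid treatment comparison. The documents do not support that: contrasts at and among the post-quit windows are unaffected, and the timing of the windows alone does no harm without empty or nearly empty cells. A reader might also infer that self-report at +3 and +8 will be mixed with verified status at +16, confounding time with definition. The plan does not say this. TLFB self-report throughout is a natural reading, so this part is mainly a clarification.

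Finally, restricting to three times is no complete cure. At 10% abstinence in both arms, about 17% of trials with 32 per arm still have an empty post-quit cell, and at 5% about 68%. With 26/22/22 observed the figures are 38% and 85%. The fix therefore needs its own empty-cell rule.

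**Conclusion.** The point holds in limited form. Two of the five abstinence windows precede the planned quit. Under a logit link with categorical time, the overall time and treatment-by-time tests are non-estimable or unreliable whenever an arm-by-window cell is empty; under linear time the slope mainly reflects quit day. Any increase in abstinence from a near-zero base cannot indicate MBRP-SA benefit, because a single quitter in either arm meets it (81 to 97% likely per arm of 32 if true abstinence is 5 to 10%). The stated definition cannot be met at +3 or +8.

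The consequences are modest: post-quit arm contrasts, per-window percentages and the Table 5 benchmarks remain sound. The conclusion rests on near-zero pre-quit abstinence, which is inferred from eligibility and the quit date. All abstinence rates in the calculations are assumptions. It is worth fixing because only wording has to change.

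**What to change.** For smoking only, state in part G, Aim 3:

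> TLFB self-reported 7-day abstinence at weeks +3, +8 and +16 will be modelled by GEE with a logit link, categorical time and AR(1) r = .60, using all observed windows and the planned sex and treatment-group terms. Numbers observed will be shown by arm and window. If any arm-by-window cell is empty, no joint Wald test will be reported; arm proportions and risk differences per window with 95% CIs (Wilson and Newcombe) will be given instead. Weeks -4 and 0 will be shown descriptively. Cotinine-verified abstinence at week 16 will be reported separately by arm with a 95% CI, with the numbers who reported smoking, were lost, returned no kit or were not confirmed.

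Using all observed windows matches the rule already given for the proximal models: "This approach preserves data for analysis by avoiding listwise deletion of observations when at least one dependent variable was observed".

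Replace the reading of any increase in abstinence with post-quit rates by arm and their 95% CIs; for example, 8 of 32 is 25% (Wilson 95% CI 13 to 42%). The heavy-drinking model keeps all five times and its interpretive wording. No earlier cotinine test is needed.

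The cost is SAP wording; the data are already collected. The one loss is that pre- to post-quit change in abstinence is no longer modelled.
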